Despite laboratory data demonstrating the potential for RLX as an immune regulating molecule via PPARG²⁸ and GCR²⁹ pathways, and its safety in the limited settings in which it has been given to humans for treatment of systemic sclerosis³⁰ and ischemic heart disease ³¹, there have been no published preclinical or clinical studies addressing potential efficacy of RLX in inflammatory CNS disease, and only one presented abstract in which it was reported that patients diagnosed with MS had higher circulating levels of RLX, and reduced binding affinity to RXFP-1, when compared to normal controls, suggesting that the increase in circulating RLX was the result of loss of RLX-RXFP-1 regulatory feedback mechanisms. Further analysis revealed that there was structural abnormality in the MS patients' RLX due to a mutation in the B- chain binding cassette of RX ([name] and [name], personal communication).

RESEARCH STRATEGY

1. Because of the potential benefits of using a human molecule, with an encouraging safety profile, capable of regulating immune responses, we intend, in the future, to develop a therapeutic trial to assess the efficacy and safety of RLX in the treatment of patients with the relapsing form of MS. However there is no information available on such fundamental guestions as what serum and CSF levels of RLX are observed in patients with active versus stable relapsing MS, how these values compare to that found in human volunteers without MS or other inflammatory diseases, and whether RLX functions normally in subjects with active or stable MS. It is for this latter reason that we are proposing research to obtain baseline information on serum and CSF RLX levels in patients with MS, as well as to further study RXFP-1 receptor binding affinity for RLX in patients with active and clinically stable MS. Fortunately there are reliable, commercially available SIMOA assays to measure RLX serum and CSF concentrations and available cell-based RXFP-1 affinity assay systems.

PROTOCOL

Subjects:

All subjects will be age 18 to 60, non-pregnant females, since 65 to 80% of MS patients are female, and there are known gender differences in circulating RLX levels. Patients with known history of diabetes will also be excluded.

There will be 3 groups of subjects:

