All subjects will sign an IRB-approved informed consent prior to undergoing any study procedures. For patients with reproductive potential, urine sample will be collected and processed with the priority of STAT for qualitative pregnancy testing. The results of the STAT urine pregnancy test will be reviewed by research staff and routed to the study physician. The LP will not proceed unless a negative urine pregnancy test is confirmed. The one exception to this will be in Group 1 patients who had already had LP performed on an emergency basis and in whom consent to analyze residual CSF and serum was obtained. In this latter instance pregnancy test result will be obtained before any relaxin analysis is performed. Every patient will provide blood sample within 24 hours before, or 24 hours after the LP. Whole blood (8-ml) will be processed and serum (5-mL) collected for study analysis. In the case of CSF removal for suspected MS (Group 1), lumbar puncture and CSF removal is not a departure from standard of diagnosis/care, however an additional 5 mL of fluid will be collected for the purpose of this study during the standard procedure. In the case of the non-MS controls (Group 3), CSF removal is a routine part of their therapy and no additional fluid will be removed (5 mL of their fluid will be used for this study). Lumbar puncture and CSF removal is not a routine part of the diagnosis or care of patients with stable MS (Group 2), and thus their informed consent would reflect the fact that they are volunteering for a clinically unnecessary invasive procedure. No patient in Group 2, with clinically stable MS, will be responsible for the costs of performing the lumbar puncture, whereas the patients in groups 1 and 3 would be having lumbar puncture in the routine course of the management of their disease, and thus the cost of the procedure should be borne by their insurer. The total volume of CSF for Group 2 is also 5 mL.

All study samples will be stored frozen before batch transport to Quanterix for testing.

Approximately 24 hours after the LP procedure research staff will contact the patient by phone to discuss any symptoms or serious adverse events. The outcome of the phone call will be routed to the physician and the patient will be encouraged to contact the study doctor with any additional questions or concerns. All SAEs will be reported the Institutional Review Board per institutional policy and guidelines.

Analysis:

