Descriptive statistics will be applied to each variable show the distribution of the data. T-tests or nonparametric tests, depending on the type and distribution of the data, will be performed to compare the differences between groups.

Results:

Patients may be informed of the results of their study testing only after the completion and analysis of all study data.

CONFIDENTIALITY:

Each volunteer subject will be assigned a unique identification number, and this will be used to identify all samples sent to the diagnostic laboratory. The subjects' names, or any other personal identification information will never be available to the diagnostic laboratory or its members.

The results of the data will be returned to the primary investigators for analysis, identified by unique code only, and only after the data has been received will the group that each sample belongs to be identified. The sole individual who knows both personal identification and code numbers will always be blinded to the analytic results and will not share the identity of any subject with the other investigators.

ASSAYS

RLX 1 is measured in serum and CSF by DuoSet (R & D Systems # DY3257) sandwich ELISA. This method is RLX 1 specific and does not cross react with RLX 2, The range of sensitivity of the assay is from 100-10000 pg/mL., and is linear within this range.

RLX 2 is measured in serum and CSF by Quantikine (R & D Systems # DRL 200) sandwich ELISA. This method is RLX 2 specific and does not cross react with RLX 1. The range of sensitivity of the assay has been demonstrated to be 7.8 to 500 pg/mL and is linear within this range.

RLX-RXFP-1 affinity is measured as a function of cAMP production in human monocyte THP-1 cells expressing RXFP-1, following incubation with RLX 1 or RLX 2, both of which act as agonist ligands for this G protein-coupled receptor.

The cAMP levels will also be determined by a commercially available cAMP assay (Flash Plate RAI 125 cAMP assay-Perkin Elmer) in the presence and absence RX neutralizing antibodies. All RLX assays will be performed at Quanterix Labs, Lexington MA.

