These analyses will provide us with quantitative data re: baseline RLXIevels in serum and CSF in subjects with and without known inflammatory CNS disease, as well as alterations in RLX receptor affinity that may occur, and determine whether there are differences in serum/CSF RLX levels and RLX receptor affinities during acute inflammatory and stable states in patients with the relapsing form of MS.

INSTITUTIONAL SUPPORT

The Providence Brain and Spine Institute's clinical research team consists of a manager, two full-time research nurses, five full-time clinical research coordinators (CRC), and 3 part-time clinical research assistants. In 2012, the team supported more than 30 active clinical trials in Alzheimer's disease, ALS, multiple sclerosis, Parkinson's disease, and stroke. The research staff has the experience and skills in conducting cooperative group trials, industry-sponsored trials, and investigatorinitiated studies. For each trial, the research staff works closely with the investigators to coordinate study activities, collect clinical research data, track patient and study status, and perform quality assurance activities regularly. The research team is familiar with clinical trials that require multiple specimen collections, diagnostic testing, and neurological and other clinical assessments. The MS Center has 4 full-time providers (5 MS neurologist and 1 NP) and a team of clinical support staff that take care of close to 3,000 MS patients. The group has successfully collaborated with industry and federally-funded sponsors, clinical research organizations, investigators, and ancillary services facilities on more than 30 MS studies in the past 5 years.

For the performance of the serum and CSF RLX and Sema4A levels and RXFP-1 RLX receptor affinity analyses, commercial and university laboratories will be employed as noted in the protocol.

REFERENCES

1. Weinshenker BG. Databases in MS research: pitfalls and promises. Mult Scler 1999;5:206-211.

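### Does the single mention of Sema4A and university laboratories under Institutional Support change what the study measures or tests?

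*Combined protocol and SAP*

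**What the plan says.** All places are in the combined protocol and SAP.

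- **Institutional Support** takes relaxin (RLX) levels, Sema4A levels and RXFP-1 affinity together. It says that for "serum and CSF RLX and Sema4A levels and RXFP-1 RLX receptor affinity analyses, commercial and university laboratories will be employed", and points back to the protocol for the detail.
- **Research Strategy** states the purpose as "we are proposing research to obtain baseline information on serum and CSF RLX levels in patients with MS", together with RXFP-1 binding affinity. It adds that commercial SIMOA assays for relaxin exist.
- **Study Procedures** gives one destination: "All study samples will be stored frozen before batch transport to Quanterix for testing".
- **Analysis** is two sentences long. "Descriptive statistics will be applied to each variable", and t-tests or nonparametric tests "will be performed to compare the differences between groups". It does not list the variables.
- **Assays** names a sandwich ELISA kit for RLX 1 (100 to 10000 pg/mL), another for RLX 2 (7.8 to 500 pg/mL), and a cAMP-based measure of receptor affinity. It says "All RLX assays will be performed at Quanterix Labs".
- The paragraph that closes Assays says the analyses will "determine whether there are differences in serum/CSF RLX levels and RLX receptor affinities during acute inflammatory and stable states". Sema4A is not mentioned.

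**The concern.** Three statements about the measurements do not line up: which analytes are measured, where, and on which platform.

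The analyte matters most to a statistician. The Analysis section applies to every variable without listing any, so the list has to be inferred from the rest of the document. If Sema4A counts, it enters the group comparisons with no stated question, assay or quantifiable range. Two analysts could then arrive at different numbers of tests in a study with 10 subjects per group.

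The laboratory and platform statements matter for a related reason. The ranges in Assays apply only if those ELISAs are the assays actually run. The platform also determines how many values fall below the lower limit, and so bears on the choice between a t-test and a nonparametric test.

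**Working it through.** The main check is textual. The plan gives no figure to reproduce.

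**1. Analyte.** Sema4A appears once in the text examined, in Institutional Support. It does not appear in the background, Research Strategy, subject groups, Study Procedures, Analysis, Assays, the closing statement of what the analyses will provide, or any of the 31 reference titles. Everything needed to run a relaxin measurement (kit, range, fluid, laboratory) is given. Nothing needed to run a Sema4A measurement is given.

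**2. Laboratory.** Study Procedures and Assays agree on one named commercial laboratory. Institutional Support conflicts only in the plural and in the word for university laboratories, and it refers the reader back to the protocol for the detail. Study Procedures sends every sample to the one laboratory, so no material is allotted to a second.

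**3. Platform.** Research Strategy says that SIMOA assays can be obtained. It does not say that they will be used. Assays says directly what is measured, with which kit and over what range. The specific statement governs the general one.

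**4. Nature of the odd sentence.** It stands in an account of staffing and capacity. That account dates its trial count to 2012 and gives 4 full-time providers while itemising 5 neurologists and 1 nurse practitioner. This reads as loosely maintained descriptive text, not as a procedure.

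**5. What the literal reading would do to the number of tests.**

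- Concentration variables under Assays: 2 isoforms × 2 fluids = 4. With Sema4A in two fluids: 4 + 2 = 6.
- Three pairs of groups: 4 × 3 = 12 tests, or 6 × 3 = 18.
- Chance of at least one p < 0.05 under no difference, active against stable MS only, independent variables, 5% level assumed: 1 − 0.95^4 = 0.185 against 1 − 0.95^6 = 0.265, a gap of 8.0 points.
- All three pairs, simulated with 10 per group and t-tests: about 40% against 55% if the variables are independent, 36% against 44% at correlation 0.5, and 27% against 32% at 0.8.

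**6. Why those figures do not measure this slip.**

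- The first figure in each pair arises without Sema4A. It reflects many tests with no multiplicity rule, which is a separate matter. Removing the word leaves it unchanged.
- Receptor-affinity variables are left out above. They add equally to both counts but not equally to both probabilities. If two affinity variables are assumed, the single-comparison figures become 1 − 0.95^6 = 0.265 against 1 − 0.95^8 = 0.337, a gap of 7.2 points. For all pairs with independent variables, simulation gives 55% against 65%.
- The documents state no significance level and do not say that all three pairs will be tested. Both are assumptions.

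**The case for a change.** The strongest case for a change is that the Analysis section is the whole statistical plan and does not enumerate its variables. The analyst must therefore take the list from elsewhere, and Institutional Support is part of the same document. On that view the sentence is a commitment to measure Sema4A with its specification missing, and correcting it costs only wording. The pointer to the protocol leads to nothing in the sections that should contain it.

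Part of this stands. The wording is inconsistent and the cross-reference, as far as the text examined goes, is unfulfilled. If the investigators do intend to measure Sema4A, the document lacks an assay and an analysis line for it.

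The step from there to different analyses does not stand. A team cannot run an assay for which it has no kit, range, laboratory or allotted sample, so the practical result is a query to the investigator. The stated aims, before and after the methods, concern relaxin and its receptor only.

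How values below an assay floor should be coded is a fair question for any immunoassay study, but it does not follow from this mismatch. The share of such values is unknown, and the Analysis section already allows nonparametric tests according to the distribution.

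**Conclusion.** This is a clerical slip, and no change to the plan is needed. Leftover wording is the most natural reading of the Sema4A and university-laboratory references. The SIMOA remark is a statement of availability that differs from the method chosen.

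The effect on results is nil for a team that follows Study Procedures, Analysis and Assays: same analytes, same laboratory, same ELISAs, same 4 concentration variables plus receptor affinity. Reconciling the wording would not correct a wrong rule or figure.

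The conclusion rests on two assumptions. First, the sections that specify procedures, assays and analysis take precedence over a description of resources that itself defers to the protocol. Second, the opening part of the document, which was not available for this check, does not set out a Sema4A objective. If it does, Sema4A would be a study variable without an assay or analysis line, and the question would need to be reopened.
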